## **Study Protocol**

A total of 60 lower impacted wisdom teeth were extracted from 30 patients participating in the study. The study was conducted as a randomized controlled trial (closed envelope method). One mucosal or bone retention fully impacted wisdom tooth was extracted from each patient at a time. The tooth extraction on the other side of the same patient was performed 3 weeks later after postoperative complications were eliminated and the extraction site wound healed and the mouth opening returned to its previous value. Patients whose extraction sites did not heal were not included in the study. The wound closure technique to be applied to the tooth to be extracted was randomly decided by the closed envelope method. The side to which suture was applied after tooth extraction was determined as the control group, and the side to which cyanoacrylate tissue adhesive (Periacryl 90) was applied was determined as the experimental group.

All operations were performed by the same dentist. In Group 1, a full thickness gingival flap was lifted to reach the first tooth to be extracted and after the procedure, the gingiva was sutured with silk in the starting position, while in Group 2, the lifted full thickness flap of the second tooth to be extracted was brought to the starting position and tissue adhesive (Periacryl 90) was applied.

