## **Surgical Technique and Application**

The patients in the study were operated on by the same physician in the local operating room environment at the XXX University, Faculty of Dentistry, Department of Oral, Dental and Maxillofacial Surgery, in accordance with the rules of asepsis and antisepsis. It was planned to extract one mandibular wisdom tooth with mucosal or bone retention from each patient at a time. The tooth extraction on the other side was performed after the postoperative complications were eliminated and the extraction site wound healed and the mouth opening was restored. The wound closure technique to be used in the tooth extraction was determined by the closed envelope method and the surgical procedure was completed using a different technique in the other tooth extraction.

The oral cavity was cleaned with an antiseptic solution before surgery and the surgical field was prepared in accordance with aseptic conditions. Demographic data, preoperative mouth opening, facial landmark measurements, data regarding the impacted tooth and the operation were recorded in the anamnesis form. Inferior alveolar block anesthesia was performed with direct technique using 3 cc articaine hydrochloride 80 mg- Epinephrine 0.010 mg/ampule (Maxicaine VEM, Turkey) with 27 gauge dental syringes. The same equipment and local anesthetic were used for buccal anesthesia. Winter type envelope flap was preferred using a scalpel tip of No. 15 in the surgeries. Following the incision, the full thickness flap was lifted to reach the extraction area. In teeth with bone retention, the bone was lifted with a 1.6 mm diameter steel rond bur, fissure bur, surgical micromotor operating at 40,000 rpm and serum irrigation, and then the teeth were exposed. Then, the teeth were extracted with the help of a bein elevator. Irrigation was performed with physiological serum to prevent the heat generated during the bone removal procedure from damaging the living tissues. Teeth that could not be extracted in one piece due to their position were divided and extracted with a surgical micromotor. After extraction, the dental follicle was removed from the alveolar region with the help of curettes and clamps. The extraction socket and the bottom of the

mucoperiosteal flap were irrigated with plenty of physiological serum to remove bone particles and tissue residues.

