## **Statistical Analyses**

While evaluating the findings obtained in the study, NCSS (Number Cruncher Statistical System) 2020 Statistical Software (NCSS LLC, Kaysville, Utah, USA) program was used for statistical analyses. While evaluating the study data, quantitative variables were shown with mean, standard deviation, median, min and max values, and qualitative variables were shown with descriptive statistical methods such as frequency and percentage. Shapiro Wilks test and Box Plot graphics were used to evaluate the conformity of the data to normal distribution.

Student t-test was used in quantitative two-group evaluations showing normal distribution.

Mann Whitney-U test was used in the evaluations of variables not showing normal distribution according to two groups.

In intra-group comparisons according to follow-ups, Paired Samples test and Repeated Measures test were used in post hoc comparisons of variables showing normal distribution, and Bonferroni test was used.

Pearson Chi-Square test, Fisher's Exact test and Fisher Freeman Halton test were used in the comparison of qualitative data.

The results were evaluated at a 95% confidence interval and significance was at  $p < 0.05$ .

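### The plan specifies no suture-versus-adhesive difference, ties its 95% confidence interval to no estimate, and compares the closures with unpaired tests although every patient receives both

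*Combined protocol and SAP*

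**What the plan says.** The design is split-mouth. Study Protocol states that "A total of 60 lower impacted wisdom teeth were extracted from 30 patients participating in the study", and Surgical Technique and Application adds that "the surgical procedure was completed using a different technique in the other tooth extraction". The suture side is the comparator: "The side to which suture was applied after tooth extraction was determined as the control group". The adhesive side is the experimental group.

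Statistical Analyses gives the outputs. For measurements, "quantitative variables were shown with mean, standard deviation, median, min and max values"; for categories, "qualitative variables were shown with descriptive statistical methods such as frequency and percentage". The tests for comparing two groups are given as "Student t-test was used in quantitative two-group evaluations showing normal distribution" and "Mann Whitney-U test was used in the evaluations of variables not showing normal distribution according to two groups". Categorical data go to chi-square, Fisher or Fisher-Freeman-Halton tests. A paired-samples test is named only for comparing follow-up times within a group. The section ends with "The results were evaluated at a 95% confidence interval and significance was at" p < 0.05.

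None of the sections names a mean, median or risk difference between the closures, a margin, or a basis for the sample size.

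**The concern.** When a new closure is compared with a standard one, the reader needs to know how far apart the two are and how precisely that is known. The plan names an interval but attaches it to no quantity, and the only outputs it lists are per-group summaries and tests. A p-value of 0.05 or more from 30 pairs would then be hard to read, because it fits both no difference and a moderate difference in either direction. A p-value below 0.05 would show that a difference exists without saying whether it is large enough to matter.

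The pairing adds to the problem. Because both closures are used in the same patient, the natural quantity is the within-patient difference. Per-group means can be subtracted by hand. The paired interval, however, needs the SD of the differences (or the within-patient correlation), and for yes/no outcomes it needs the discordant counts. Neither is among the listed outputs. An interval taken from the named two-group tests would ignore the pairing.

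**Working it through.** **Inputs from the documents.** 30 patients and 60 teeth (Study Protocol), so 60 / 2 = 30 pairs, which agrees. Threshold p < 0.05 and a 95% level (Statistical Analyses). The plan states no power, effect size, SD or margin, so it has no figure of its own to reproduce.

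**Assumptions.** Two-sided testing; the same outcome SD on both sides; all 30 pairs complete; within-patient correlation r between 0 and 0.7. Results are in units of the outcome SD.

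**Half-width of the 95% interval, unpaired t-test as named**

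t(0.975, 58) × √(2/30) = 2.002 × 0.258 = **0.52 SD**

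**Half-width, paired analysis**

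t(0.975, 29) / √30 = 2.045 / 5.477 = 0.373 SD of the within-patient difference. Multiplying by √(2(1 − r)) converts this to outcome SD units.

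| r | √(2(1 − r)) | Half-width (SD) | Difference detectable with 80% power (SD) | Power for a true 0.5 SD difference |
|---|---|---|---|---|
| 0 | 1.414 | 0.53 | 0.75 | 47% |
| 0.3 | 1.183 | 0.44 | 0.63 | 61% |
| 0.5 | 1.000 | 0.37 | 0.53 | 75% |
| 0.7 | 0.775 | 0.29 | 0.41 | 93% |

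Power is from the noncentral t distribution. The detectable difference is 0.529 SD of the within-patient difference, multiplied by the same factor.

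For the unpaired t-test the nominal figures, which treat the two sides as independent, are 0.74 SD detectable with 80% power and 48% power for a true 0.5 SD difference. The second figure hardly depends on independence. An observed difference must exceed about 0.52 SD to be significant, so a true difference of 0.5 SD would fall short about half the time.

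**Reading a null result.** If the estimated difference were zero, the interval would still include true differences of about 0.3 to 0.5 SD either way, depending on the analysis and on r.

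**Could 30 pairs support a similarity claim?** With no true difference, one-sided 0.025, 80% power and an assumed margin m, the number of pairs is 2(1 − r) × (1.960 + 0.842)² / m².

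- m = 0.5 SD: 63, 44, 32 and 19 pairs at r = 0, 0.3, 0.5 and 0.7.
- m = 0.3 SD: 175, 123, 88 and 53 pairs.

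Thirty pairs would therefore be enough in some of these settings and not in others.

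**The case against.** The strongest case against the point has four parts.

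- **An interval is named.** A reader might infer that the closures are judged on the p-value alone. The text does not support that, because the closing sentence mentions a 95% confidence interval. It may mean only the confidence level, but that is an inference. What stands is that the interval is attached to no estimate.
- **No similarity aim is stated.** A reader might infer that the trial set out to show that adhesive performs as well as suture, and that it fails to do so. The sections available state no equivalence or non-inferiority aim and no rule that treats non-significance as similarity. Control and experimental labels fit a superiority question equally well. This part stands in full.
- **Silence is not evidence of what was reported.** The section names summaries and tests, and it does not say that nothing else was tabulated. A reader might infer that no difference was ever reported, but the text shows only that none is specified.
- **Per-group means and SDs with n = 30 do give an interval for the planned unpaired t-test.** This is true. That interval ignores the pairing, though, and the paired interval cannot be recovered from the listed outputs.

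It can also be said that the deeper fault is the use of unpaired tests, and that the missing estimate follows from it. The two are linked. Even so, changing the tests to paired ones would still leave the plan without a stated effect and interval.

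**Conclusion.** The point holds in a limited form. The plan specifies no between-closure effect, leaves its 95% interval unattached, and uses unpaired tests on paired data. Following it gives no within-patient difference with a valid interval.

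At an assumed correlation of 0.5, the interval would reach 0.37 SD either side in a paired analysis, against 0.52 SD from the unpaired t-test. Both are wide enough for a non-significant result to coexist with a moderate difference. The sizes rest on the assumed correlations, equal SDs and complete pairs. The t-based figures do not describe categorical or clearly non-normal outcomes.

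The point does not show that 30 pairs are too few: at r = 0.7 and an assumed margin of 0.5 SD, 19 would suffice. Only the interval shows which situation applies. It limits what a null result can mean and does not invalidate the trial.

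**What to change.** Replace the closing sentence of Statistical Analyses with a statement of what will be estimated. For each between-closure comparison, report the within-patient difference (adhesive minus suture) with its 95% confidence interval from a paired analysis, beside the p-value:

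- mean difference for roughly normal outcomes;
- median (Hodges-Lehmann) paired difference for non-normal outcomes;
- paired risk difference for yes/no outcomes. For outcomes with more than two categories, say which category or grouping the difference refers to.

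Add two rules for interpretation. A p-value of 0.05 or more is not read as similarity, and the result is called inconclusive when the interval includes differences that matter. Similarity is claimed only against a margin justified before the results are looked at.

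The cost is one extra column per results table and a re-run of the comparisons on data in which both sides of each patient are already included. No new patients or visits are needed. The downside is that some statements of no difference will become inconclusive.
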